#### **3.7.1.6 Week 1 Examination ( $\pm 2$ Days)**

The investigator or subinvestigator will perform the following examinations, observations, and evaluations and record the results in the source document and CRF.

- Physical examination
- Vital signs (including body weight)
- IGA
- EASI
- VAS for pruritus (only for 7 - 14 years of age)
- POEM
- Affected BSA
- Blood sampling for plasma drug concentration measurement
- Adverse events

- Concomitant medications and therapies
- Status of IMP Administration

The investigator or subinvestigator will determine the treatment area (%) and enter it in the IWRS. Also, the investigator or subinvestigator will confirm the subject's allocation status on the IWRS screen and, if necessary, prescribe additional IMP. When the IMP is additionally prescribed, the weight of the dispensed IMP will be measured.

#### **3.7.1.7 Week 2 Examination ( $\pm 3$ Days)**

The investigator or subinvestigator will perform the following examinations, observations, and evaluations and record the results in the source document and CRF.

- Physical examination
- Vital signs (including body weight)
- IGA
- EASI
- VAS for pruritus (only for 7 - 14 years of age)
- POEM
- Affected BSA
- Adverse events
- Concomitant medications and therapies
- Status of IMP Administration

The investigator or subinvestigator will collect the IMP and measure the weight of the collected IMP. The investigator or subinvestigator will determine the treatment area (%) and enter it in the IWRS. The investigator or subinvestigator will confirm the amount of IMP to be prescribed for the next 2 weeks and prescribe it. The weight of the dispensed IMP will be measured. The subjects will be instructed to visit the trial site without morning IMP administration on the day of the next visit.

#### **3.7.1.8 Week 4 Examination ( $\pm 3$ Days) or Withdrawal Examination**

The investigator or subinvestigator will perform the following examinations, observations, and evaluations and record the results in the source document and CRF.

- Physical examination
- Vital signs (including body weight)
- 12-lead ECG (For children aged 2 - 6 years old, as much as possible. If possible, it will be conducted prior to blood sampling.)

- Clinical laboratory tests
- Pregnancy test (only for female children aged 7 - 14 years old)
- IGA
- EASI
- VAS for pruritus (only for 7 - 14 years of age)
- POEM
- Affected BSA
- Blood sampling for plasma drug concentration measurement
- Adverse events
- Concomitant medications and therapies
- Status of IMP Administration

The investigator or subinvestigator will collect the IMP and measure the weight of the collected IMP.

#### **3.7.1.9 Examination 2 Weeks After Last IMP Administration ( $\pm 7$ Days)**

The investigator or subinvestigator will perform the following examinations, observations, and evaluations and record the results in the source document and CRF.

- Physical examination
- Adverse events

#### **3.7.1.10 Unscheduled Visits**

The investigator or subinvestigator will instruct the subjects to visit the trial site if the area of affected BSA markedly enlarges. The investigator or subinvestigator will perform the following examinations, observations, and evaluations and record the results in the source document and CRF.

- Affected BSA
- Adverse events
- Concomitant medications and therapies

The followings can be evaluated, as necessary.

- Physical examination
- Vital signs (including body weight)
- 12-lead ECG
- Clinical laboratory tests

- Pregnancy test

The investigator or subinvestigator will determine the treatment area (%) and enter it in the IWRS. Also, the investigator or subinvestigator will confirm the subject's allocation status on the IWRS screen and, if necessary, prescribe additional IMP. When the IMP is additionally prescribed, the weight of dispensed IMP will be measured.

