6.4 Study Week Windows

The definitions of timepoints for analysis are described in Table 6.4-1 and Table 6.4-2. Timepoints, including unscheduled visits and visit at discontinuation, will be determined based on the number of days from the start of IMP administration. However, for Verbal Rating Scale (VRS), the timepoint will be determined based on the amount of time that has elapsed from the start of IMP administration. For efficacy variables, the data obtained between the day of the start of IMP administration and 7 days after the last IMP administration will be used in analyses. If multiple data exist within the allowable window of the timepoint, the data obtained last will be used for analyses. Data for the Last Visit will be defined as the last data obtained between the day of the start of IMP administration and 7 days after the last IMP administration (including data obtained at discontinuation) for efficacy variables or as the last data obtained after the start of the IMP administration for safety variables.

In analyses, baseline data will be defined as data obtained on the day or at the date and time before and nearest to the start of IMP administration, including the screening data.

Table 6.4-1 Timepoints and Allowable Windows for Efficacy Variables (Except VRS) and Safety Variables				
Timepoint	Study Day	Allowable Window (Days After the Start of IMP Administration)		
Week 1	8	1	-	10
Week 2	15	11	-	21
Week 4	29	22	-	43

Table 6.4-2 Timepoints and Allowable Windows for VRS			
Timepoint	Allowable Window (Hours After the Start of IMP Administration)		
Hour 4	1	-	< 6
Hour 8	6	-	< 10
Hour 12	10	-	< 18
Hour 24	18	-	< 30
Hour 36	30	-	< 42
Hour 48	42	-	< 54
Hour 60	54	-	< 66
Hour 72	66	-	< 78
Hour 84	78	-	< 90
Hour 96	90	-	< 102
Hour 108	102	-	< 114
Hour 120	114	-	< 126
Hour 132	126	-	< 138
Hour 144	138	-	< 150
Hour 156	150	-	< 162
Hour 168	162	-	< 174

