10.1.6 Change From Baseline in Overall Percentage Affected BSA

The change from baseline in overall percentage affected BSA will be analyzed in the same manner as that in the overall EASI score or each EASI symptom score.

10.1.7 Percent Changes From Baseline in Overall EASI Score, EASI Symptom Scores, VAS for Pruritus, and POEM Scores

The percent changes from baseline in overall EASI score, EASI symptom scores, EASI scores for body regions, VAS for pruritus, and POEM score will be analyzed in the same manner as the changes from baseline in the respective scores.

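### The last-in-window rule lets an affected BSA reading taken because the area enlarged replace a completed Week 1 or Week 2 reading

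*Protocol*

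**What the plan says.** **When an unscheduled visit happens.** Protocol 3.7.1.10 has the investigator "instruct the subjects to visit the trial site if the area of affected BSA markedly enlarges".

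**What is measured there.** The required items are affected BSA, adverse events, and concomitant medications and therapies. A second list opens with "The followings can be evaluated, as necessary" and holds only physical examination, vital signs, ECG, laboratory tests and pregnancy test. Table 3.7-1 agrees: affected BSA is marked in the unscheduled-visit column, while IGA, EASI, VAS and POEM are not.

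**How those readings enter the analysis.** SAP 6.4 states: "Timepoints, including unscheduled visits and visit at discontinuation, will be determined based on the number of days from the start of IMP administration". It continues: "If multiple data exist within the allowable window of the timepoint, the data obtained last will be used for analyses". The windows in Table 6.4-1 are Days 1-10 for Week 1, 11-21 for Week 2 and 22-43 for Week 4. Nothing in either document prefers a scheduled reading over an unscheduled one.

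**What is done with them.** SAP 10.1.6 says: "The change from baseline in overall percentage affected BSA will be analyzed in the same manner as that in the overall EASI score". By reference to SAP 10.1.2, this means MMRM and ANCOVA contrasts with confidence intervals and p-values at Weeks 1, 2 and 4 (tables CT-5.5.1 to CT-5.5.3). The Protocol synopsis names Week 4 as the timepoint of the affected BSA endpoint.

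**The concern.** The event that produces the extra reading is worsening of the variable being analysed. A child whose eczema spreads soon after the Week 2 examination is called in and measured again, and the new value becomes the Week 2 value. A child who stays stable or improves has no matching reason for an extra visit and keeps the scheduled value. Which reading is analysed therefore depends on the outcome.

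Two things follow at Weeks 1 and 2:

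- The mean affected BSA in an arm is pushed upward by the share of its children who are called in. If that share differs by arm, the between-arm difference is amplified.
- For a child who continues treatment, affected BSA comes from a different day than IGA, EASI, VAS and POEM under the same timepoint label. EASI has its own area component, so the two scales can disagree merely because of their dates.

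**Working it through.** The plan gives no figure to reproduce here. The check is day arithmetic, followed by an illustration of size.

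**1. Days on which a completed reading can be replaced.** Exposed days = last day of the SAP window minus day of the scheduled examination. Tolerances come from Protocol 3.7.1.6 and 3.7.1.7; study days and windows come from SAP Table 6.4-1.

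| | Week 1 | Week 2 |
|---|---|---|
| Nominal day and tolerance | 8 ± 2 | 15 ± 3 |
| Scheduled examination falls on | Day 6-10 | Day 12-18 |
| SAP window | Day 1-10 | Day 11-21 |
| Exposed days, nominal visit | 10 − 8 = 2 | 21 − 15 = 6 |
| Exposed days, earliest visit | 10 − 6 = 4 | 21 − 12 = 9 |
| Exposed days, latest visit | 10 − 10 = 0 | 21 − 18 = 3 |

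If the window is instead counted with the first treatment day as day 0, nominal visits fall on days 7 and 14. The ranges become 1-5 days (10 − 9 to 10 − 5) and 4-10 days (21 − 17 to 21 − 11). The conclusion is the same.

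Only an unscheduled visit after the scheduled one and inside the same window replaces it. One that comes earlier in the window is itself superseded.

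**2. Week 4.** The window runs to Day 43 and the examination falls on Day 26-32 (29 ± 3), so by days alone there would be room for replacement. But Table 3.7-1 places unscheduled visits in the assessment period, and Protocol 3.1 ends that period at the Week 4 examination. A completed Week 4 reading is therefore the last one. An unscheduled reading from Day 22 onward stands as Week 4 only if that examination is missed. LOCF can likewise carry a replaced Week 2 value forward only when Week 4 has no value.

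**3. Size, on assumed inputs.** Neither document gives the frequency of such visits or the amount of enlargement. Assume:

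- f_V = 5-15% of vehicle children with a replaced reading (1 to 3 of 20)
- f_A = 0-5% of active children with a replaced reading (0 to 1 of 20)
- d = 5-10 BSA points by which the unscheduled reading exceeds the one it replaces

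Shift in the between-arm difference = (f_V − f_A) × d.

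- Smallest: (0.05 − 0.05) × 5 = 0
- Largest: (0.15 − 0) × 10 = 1.5 BSA points
- One child in an arm of 20, reading 10 points higher: 10 / 20 = 0.5 points on that arm's mean

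These inputs put at least as many replaced readings on vehicle as on active. That ordering is part of the assumption.

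**4. After the fix.** With scheduled values given precedence, the number of exposed days is 0 at both weeks.

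**The case against.** The case for leaving the rule alone has substance. The rule is prespecified, it is the same in every arm, and the readings are blinded. With no treatment effect, such visits would be expected equally often in each arm, so no spurious difference is expected. The values are real on-treatment measurements, and taking the last value in a window is a recognised convention. Affected BSA is only one of several secondary scales in a 60-subject trial whose primary endpoint is adverse events. All of this stands, and it is why the point is minor. It does not answer the selection itself: the stated rule discards a planned reading in favour of one prompted by worsening.

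A reader might infer more than the documents support, in three ways.

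- **That readings can be replaced only by worse ones.** This is too absolute. Marked enlargement brings the family in, but the measured value need not exceed the scheduled one. SAP 6.4 also slots discontinuation visits, which can replace a reading in either direction. Predominantly worse is as far as the text goes.
- **That the Week 4 estimate is biased through the MMRM.** The model has its own treatment means at each visit and an unstructured covariance. For children with Week 4 data, earlier values reach the Week 4 contrast only through the shared baseline slope. They matter mainly when Week 4 is missing. The observed-case ANCOVA at Week 4 does not use them at all.
- **That the effect flatters the drug.** Protocol 1.2.4 reports discontinuations for dermatitis atopic in trial 271-12-205: 3 on vehicle, 1 on 0.3% and 2 on 1%. With denominators implied by the stated percentages, these are 3/37 = 8.1%, 1/41 = 2.4% and 2/43 = 4.7%. The counts are very small, cover 8 weeks in patients aged 10-70, and concern discontinuation rather than enlargement visits. They do not establish a direction for this trial.

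The mismatch of dates is limited too. Where the visit leads to discontinuation of treatment, the withdrawal examination records all the scales, so the mismatch concerns children who continue.

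**Conclusion.** The point holds as a minor flaw in the data-selection rule. Read together, Protocol 3.7.1.10, Table 3.7-1 and SAP 6.4 let a completed affected BSA reading be replaced by a later, worsening-triggered one, over 0-4 days at Week 1 and 3-9 days at Week 2. The planned Week 1 and Week 2 contrasts for affected BSA are exposed to this.

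The effect on the between-arm difference is 0 to 1.5 BSA points under the assumed inputs and rests entirely on them. The named Week 4 endpoint is essentially unaffected when the Week 4 examination is done. The primary safety endpoint is not involved, and neither is IGA success, because IGA is not taken at these visits.

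**What to change.** Add to SAP 6.4, for affected BSA only:

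- Use the scheduled-examination value whenever the window holds one.
- Use an unscheduled value only when the window holds neither a scheduled nor a withdrawal value.
- Leave withdrawal-examination data under the existing last-value rule, as for the other scales.
- List the unused unscheduled values; the planned listing PDATA-18 can carry them.

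The cost is one sentence in the SAP and one programming condition. No visit, measurement or clinical procedure changes, and every reading is still reported. SAP section 4 has the plan finalised before database lock, so the change can be made without sight of unblinded results.

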### 3.7.2 Status of IMP Administration

Details of the administration diary will be recorded in the CRF. If the frequency of compliance with IMP administration is less than 80%, the status of IMP administration is judged as poor. The investigator and subinvestigator will confirm the status of IMP administration based on records in the administration diary and instruct the subjects, as necessary.

### 3.7.3 Severity

The investigator or subinvestigator will determine the severity (mild, moderate, severe, or very severe) and record the result in the source document and CRF.

Definition	Severity
Just mild skin eruption regardless of the area	Mild
Skin eruption with severe inflammation on <10% of the BSA	Moderate
Skin eruption with severe inflammation on ≥10% to <30% of the BSA	Severe
Skin eruption with severe inflammation on ≥30% of the BSA	Very severe

Mild skin eruption: lesions mainly consisting of mild erythema, dryness, or desquamation

Skin eruption with severe inflammation: lesions consisting of erythema, papules, erosion, infiltration, or lichenification

### 3.7.4 Efficacy Assessments

#### 3.7.4.1 Investigator's Global Assessment (IGA)

The investigator or subinvestigator will assess the skin symptoms using IGA. The investigator or subinvestigator will score the severity (0 = clear, 1 = almost clear, 2 = mild, 3 = moderate, 4 = severe/very severe) of the overall symptoms of the treatment area (erythema, infiltration, papules, effusion, and scab formation). The result will be recorded in the source document and CRF. The same subject will be evaluated by the same physician, as much as possible.

Symptom	Severity score
No inflammatory signs of AD	0 = Clear
Just perceptible erythema and just perceptible papulation/infiltration	1 = Almost clear
Mild erythema and mild papulation/infiltration	2 = Mild

Symptom	Severity score
Moderate erythema and moderate papulation/infiltration	3 = Moderate
Severe erythema and severe papulation/infiltration with oozing/crusting	4 = Severe/very severe

### 3.7.4.2 Eczema Area and Severity Index (EASI)

The investigator or subinvestigator will assess the skin symptoms using EASI. The investigator or subinvestigator will score the severity (0-3 points) and affected BSA (%) based on the 4 symptoms (erythema, infiltration/papules, excoriation, and lichenification) on the 4 body regions (face, neck, and head; upper limbs; trunk; and lower limbs) and record the results in the source document and CRF. As shown in the table below, the score of each region will be calculated and totalized. The maximum EASI score is 72 points. The same subject will be evaluated by the same physician, as much as possible.

Body region	Calculation of the score for each region
Face, neck, and head	$(E + I + Ex + L) \times \text{score of affected BSA} \times 0.1$ ( $\times 0.2$ for children aged 2-7 years old)
Upper limbs	$(E + I + Ex + L) \times \text{score of affected BSA} \times 0.2$
Trunk	$(E + I + Ex + L) \times \text{score of affected BSA} \times 0.3$
Lower limbs	$(E + I + Ex + L) \times \text{score of affected BSA} \times 0.4$ ( $\times 0.3$ for children aged 2-7 years old )

E = severity score of erythema; I = severity score of infiltration/papules; Ex = severity score of excoriation; L = severity score of lichenification

Severity score: clear = 0; slight = 0.5; mild = 1; mild-moderate = 1.5; moderate = 2; severe = 2.5; very severe = 3

Score of affected BSA (for each region): clear = 0; 1% to 9% = 1; 10% to 29% = 2; 30% to 49% = 3; 50% to 69% = 4; 70% to 89% = 5; 90% to 100% = 6

### 3.7.4.3 Visual Analogue Scale (VAS) for Pruritus

The investigator or subinvestigator will evaluate the level of pruritus based on VAS. The subjects aged 7 to 14 years old will mark the point of pruritus intensity during the last 24 hours on the line of a 100-mm VAS sheet (Appendix 2) between the left end (no pruritus) and the right end (very severe pruritus). The investigator or subinvestigator will record the length from the left end to the mark (integer value with mm as unit) in the medical record and CRF. The VAS sheet will be kept as the source document. For subjects aged 2 to 6 years, this will not be evaluated.

### 3.7.4.4 Verbal Rating Scale (VRS) for Pruritus

The investigator or subinvestigator will evaluate the pruritus intensity based on VRS. The subjects aged 7 to 14 years old will evaluate the pruritus intensity according to the following criteria. The subjects will record the level of pruritus and the time and date of evaluation in a pruritus diary.

0: None

1: Mild

2: Moderate

3: Severe

The investigator or subinvestigator will record details of the pruritus diary in the CRF. The pruritus diary will be kept as the source document. For subjects aged 2 to 6 years, this will not be evaluated.

#### **3.7.4.5 Patient-Oriented Eczema Measure (POEM)**

The investigator or subinvestigator will evaluate eczema according to the POEM (Appendix 3). The subjects will answer 7 questions about their eczema. If it is difficult for subjects to answer the questions, their parents will answer them instead. The investigator or subinvestigator will record the results in the source document and CRF. The total score of POEM is 28 points at the most.

#### **3.7.4.6 Affected BSA**

The investigator or subinvestigator will draw the affected BSA (range of skin eruption at the time of examination) on the human body drawing (Appendix 4 for subjects aged 8 to 14 years old, or Appendix 5 for subjects aged 2 to 7 years old) to determine the affected areas (%) on the respective 4 body regions (face, neck, and head; upper limbs; trunk; and lower limbs). The respective affected areas (%) will be recorded in the source document and CRF. One palm of the subject corresponds to 1% BSA.

### **3.7.5 Safety Assessments**

#### **3.7.5.1 Adverse Events**

Refer to “5 Reporting of Adverse Events.”

#### **3.7.5.2 Clinical Laboratory Tests**

The investigator or subinvestigator will perform clinical laboratory tests for the following items. Date of blood and urine sampling will be recorded on the source document and CRF.

- Hematology: differential white blood cell count (neutrophils, lymphocytes, monocytes, eosinophils, basophils), white blood cell count, red blood cell count, hemoglobin, hematocrit, platelets

- Serum chemistry: total cholesterol, total protein, albumin, blood urea nitrogen, creatinine, total bilirubin, AST (GOT), ALT (GPT), gamma glutamyl transpeptidase, lactic dehydrogenase, alkaline phosphatase, serum electrolytes (Ca, Na, K, Cl)
- Qualitative urinalysis: glucose, protein

The tests will be performed at the central laboratory. The investigator or subinvestigator will confirm the test results from the central laboratory, put the date and his or her printed name and personal seal or signature on the report from the clinical laboratory, and retain it for each subject as the source document. The central laboratory will send the test results to the sponsor (in the form of electronic data).

The total blood volume to be drawn for the clinical laboratory tests is about 10 mL during the trial period (about 5 mL each for the screening examination and for the Week 4 examination).

For female children aged 7 to 14 years old, a pregnancy test will be performed, and the result must be obtained prior to the IMP administration.

### **3.7.5.3 Physical Examination**

The investigator or subinvestigator will assess the subject's physical condition by interview, visual examination, auscultation, or palpation.

### **3.7.5.4 Vital Signs (Including Body Weight)**

After the subject has rested for 3 minutes or more in principle, body temperature (measured by 0.1°C in the armpit), blood pressure (systolic/diastolic), pulse rate, and body weight (measured to one decimal place in unit of kilogram) will be measured, and the results of measurement will be recorded in the source document and CRF.

### **3.7.5.5 12-Lead ECG**

After the subject has rested for 10 minutes or more in a supine position, 12-lead ECG will be recorded prior to blood sampling, as much as possible. Also, for subjects aged 2 to 6 years old, it will be conducted before blood sampling, if possible. For the ECG measurement, heart rate, RR interval, PR interval, QRS interval, QT interval, and QTc interval will be measured, using a 12-lead electrocardiograph obtained from the central ECG reading facility. The measurement results will be analyzed at the central ECG reading facility. The investigator or subinvestigator will confirm the "12-lead ECG analysis report" from the central ECG reading facility, assess whether the ECG results are normal or abnormal, and record the time and date of the measurement, assessment result, and findings in the source document and CRF. Then, the investigator

or subinvestigator will put the confirmation date and his or her printed name and personal seal or signature on the “12-lead ECG analysis report” from the central ECG reading facility and retain it for each subject as the source document.

If IMP randomization is necessary before the results from the central ECG reading facility are available, the automated analysis results of the 12-lead electrocardiograph at baseline (same as the ECG data to be sent to the central ECG reading facility) may be used for judgment of subject’s eligibility. In that case, the investigator or subinvestigator will put the confirmation date and his or her printed name, and personal seal or signature on the automated analysis results of the 12-lead electrocardiograph and retain it as the source document.

The central ECG reading facility will send the 12-lead ECG analysis results (in electronic data format) to the sponsor.

